### 11.4.1 Analysis of the Primary Hypothesis

The primary statistical analysis to evaluate the primary hypothesis will use all data from the intention-to-treat analytical sample in a linear mixed model. During the analysis of the primary hypothesis, treatment allocation will be masked (i.e., groups will be labeled A and B). Treatment allocation will be unmasked for further analyses.

---

The dependent variable will be the participant's change in the weekly pain index, computed as the weekly pain index at the follow-up visit (i.e., at Visit 2, Visit 3, or Visit 4) minus the Visit 1 weekly pain index. Explanatory variables will comprise fixed factors and a continuous covariate. The fixed factors will include the following: (a) treatment allocation (two categories) (b) visit sequence (three categories); (c) interaction of treatment allocation and visit sequence (two dummy variables); and (d) covariates of study site (three categories), sex (two categories) and race/ethnicity (probably three categories: non-Hispanic White, non-Hispanic Black, and other/multiple racial or ethnic groups – the final number of conditions will be dictated by the frequency distribution of race/ethnicity in the study sample). The baseline score collected at Visit 1 will be the continuous covariate, modeled as a fixed effect. The study participant will be modeled as a random factor.

In a linear mixed model containing all predictor variables including the interaction terms for visit and treatment allocation, the primary treatment effect will be tested at Visit 4. The null hypothesis of no treatment effect will be rejected if the P-value at Visit 4 is  $\leq 0.05$ . For descriptive purposes (and regardless of the P-value for efficacy at Visit 4), efficacy estimates at each visit (2, 3 and 4) will be described in terms of adjusted means and 95% confidence intervals.

If the propranolol treatment arm has a greater reduction in the weekly pain index than the placebo arm at Visit 4, a threshold of "responder analysis" will be undertaken to estimate the odds of at least a 30% reduction, relative to Visit 1, in the pain index at Visit 4. Likewise, another threshold of responder analysis will describe the odds of experiencing at least a 50% reduction. These estimates will be calculated from a logistic model in which the dependent variable is a binary variable that dichotomizes the change score at the appropriate threshold (i.e.,  $\geq 30\%$  or  $\geq 50\%$ ).

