#### **11.4.2 Analysis of the Secondary Hypotheses**

To test the secondary hypothesis of gene-by-treatment interaction, the linear mixed model described for the primary analysis will be extended by adding three sets of predictor variables: (1) the number of COMT LPS haplotypes (0, 1, or 2) will be modeled as a fixed effect, either as a continuous variable, or as a 3-level categorical variable (i.e., two dummy variables), with the decision based on the approach that optimizes model fit, as determined by Akaike's Information Criterion; (2) two-way interactions between haplotype effect and treatment allocation and between haplotype effect and visit sequence; and (3) a three-way interaction term between the

---

haplotype effect, treatment allocation, and visit sequence. The gene-by-treatment interaction at V4 is the interaction of interest.

For descriptive purposes, an analogous model will generate efficacy estimates according to COMT ValMet genotype as the genetic marker instead of the number of LPS haplotype. In an analogous manner, the genotype will be coded either as a continuous or categorical variable based on optimal model fit. Efficacy estimates will be calculated for descriptive purposes only; there will be no hypothesis tests for the interaction terms.

Another descriptive set of secondary analyses will adapt the approach for analysis of the LPS haplotype, restricting the model to non-Hispanic whites. This is consistent with the approach of some genetic researchers who advocate racial-group restriction as a preferable analytic method to control for population stratification.

Linear mixed models will be used to evaluate effects of treatment group allocation on secondary efficacy variables (see Statistical Analysis Plan for full details).

Linear regression or other appropriate statistical modeling will evaluate the effects of treatment on the number of days in which rescue medications for TMD-related pain reportedly were used and on the number of days in which over-the-counter analgesics (namely, NSAIDs, acetaminophen, and aspirin) reportedly were used for treatment of any type of pain.

See the Statistical Analysis Plan for more details on these secondary analyses.

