8.3.1 Primary Efficacy Analyses

The primary statistical analysis to evaluate the primary hypothesis will use all data from the ITT analytical sample in a linear mixed model. Mixed models will be used to analyze the treatment effect at V4 (Proc Mixed, SAS, version 9.4 or greater, SAS Institute, Inc., Cary, North Carolina). The mixed model will include the net change in the mean pain index as the dependent variable. The model's independent variables will include fixed effects for site, sex, race-ethnicity, the

Version 3.0 Page 14 of 25

mean pain index at V1 (as a baseline covariate), visit (V2, V3 and V4), treatment allocation (active versus placebo), and a visit by treatment interaction. Participants will be included as a random effect in the mixed model. The mixed model will be run twice assuming either a compound symmetry or an unstructured variance structure. The mixed model achieving the lowest Akaike information criterion will be selected as the best model and used for reporting of results. The model's denominator degrees of freedom will be adjusted for any possible effects of sample imbalances due to any missing values using Kenward Roger's method in SAS. For descriptive purposes (and regardless of the P-value for efficacy at Visit 4), efficacy estimates at each visit (2, 3 and 4) will be described in terms of adjusted means and 95% confidence intervals.

If there is a treatment effect, then "responder analyses" will be performed to compare the responder status of the treatment allocation groups. Participants will have their binomial responder status classified at both the 30% and 50% response threshold levels. The odds ratios of treatment group allocation on the responder status of participants at both the 30% and 50% threshold levels will be estimated using logistic regression with covariate adjustments for site and V1 weekly mean pain index. The odds ratio for the effect of treatment allocation on responder status for both the 30% and 50% threshold levels will be reported with their 95% confidence limits and their associated P-values.

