To test the secondary hypothesis of gene-by-treatment interaction, the linear mixed model described for the primary analysis will be extended by adding three sets of predictor variables: (1) the number of COMT LPS haplotypes (0, 1, or 2) will be modeled as a fixed effect (both as a continuous variable and as a categorical variable); (2) two-way interactions between haplotype effect and treatment allocation and between haplotype effect and visit sequence; and (3) a threeway interaction term between the haplotype effect, treatment allocation, and visit sequence. The gene-by-treatment interaction at V4 is the interaction of interest. A contrast statement within the mixed model will test for a gene-by-treatment interaction at V4 with a P-value ≤ 0.05 considered statistically significant. Both an unstructured and compound symmetry variance structure, as well as, fitting the haplotype variable as a continuous (linear) and a categorical variable will be tested. The statistical model with the lowest Akaike information criterion will consider the best model and used for inference testing. Residual analysis will be used to confirm that there are no major violations of model assumptions. Model adjusted means will be reported with their 95% confidence intervals. For descriptive purposes, a second set of secondary analyses will be performed on the valine allele of the *COMT* gene using valine allele (Val/Met allele) counts in an identical manner as for the LPS haplotype counts described. A third set of secondary analyses will adapt the approach for analysis of the LPS haplotype, restricting the model to non-Hispanic whites. This is consistent with the approach of some genetic researchers who advocate racialgroup restriction as a preferable analytic method to control for population stratification.

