8.3.3 Exploratory Efficacy Analyses

The mixed model described for the secondary hypothesis of the LPS and Val/Met haplotypes will be modified by specifying genetic variants for the *COMT* promoter, *ADRB2* gene, and *ADRB3* gene. Other genetic variants may also be included in the mixed model. The only difference in these mixed model analyses is that the *ADRB2* and *ADRB3* gene types will be included as categorical fixed effects rather than the linear continuous fixed effects in the LPS and Val/Met haplotype mixed models.

Other stratum-specific estimates of treatment effect will be explored in an analogous manner, namely through the use of mixed models in which the stratification variable is a categorical fixed effect. Each stratum will be a mutually exclusive category of study participants, classified according to the following characteristics assessed either at V0 or V1:

- Body Mass Index, computed from measurements recorded at V1, will be used to create two strata, with the dichotomy based on one of two established thresholds ≥25 or ≥30. The decision as to which threshold will be made after inspecting the distribution of BMI, and select the threshold that is closest to the median.
- Smoking status, assessed using the Smoking questionnaire completed at V0, will be used to create two strata: current tobacco smokers or not (the latter therefore including former smokers and never smokers). Smokeless tobacco and other sources of nicotine will not be used for this classification.
- Migraine headache will be classified using responses to the headache questionnaire (HAQ) administered at V1. Two strata will be created, classified according to presence or absence of one or more of four types of migraine sub-types (Migraine without aura, Migraine with aura, Chronic migraine, or Probable migraine without aura).
- Degree of examiner-assessed tenderness to body palpation, recorded at Item 4 of the Fibromyalgia Questionnaire at V0, will be used to create two strata, based as closely as possible on a median split of the total number of tender points.

Version 3.0 Page 17 of 25

- Published scoring algorithms will be used to compute the catastrophizing subscale of the revised Coping Strategies Questionnaire (CSQ-R) measured at V1. The two strata will be based as closely as possible on a median split of the subscale score.

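### The AIC choice between linear and 3-level COMT coding names neither ML nor REML; under REML, at the plan's 0-10,000 scale, it picks 3-level coding whatever the fit

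*SAP*

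**What the plan says.** - **Coding.** Protocol 11.4.2 allows the number of LPS haplotypes (0, 1 or 2) to enter as a continuous variable or as a "3-level categorical variable (i.e., two dummy variables"), "with the decision based on the approach that optimizes model fit", judged by AIC.
- **Selection.** SAP 8.3.2 compares compound symmetry with unstructured covariance and adds that "fitting the haplotype variable as a continuous (linear) and a categorical variable will be tested". That makes four candidate models in one comparison. The rule is: "The statistical model with the lowest Akaike information criterion will consider the best model and used for inference testing".
- **Test.** SAP 8.3.2 says: "A contrast statement within the mixed model will test for a gene-by-treatment interaction at V4", with P at or below 0.05 counted as significant. It gives no coefficients or degrees of freedom.
- **Estimation.** SAP 8.3.1 names the software ("Proc Mixed, SAS, version 9.4 or greater") and the Kenward-Roger degrees of freedom. Neither document mentions ML or REML.
- **A conflicting description.** SAP 8.3.3 says the ADRB2 and ADRB3 variants will enter as "categorical fixed effects rather than the linear continuous fixed effects in the LPS and Val/Met haplotype mixed models", as though linear coding were settled.
- **Power.** Protocol 11.2 and SAP 2.6 give 61% power for the interaction without naming the test.

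**The concern.** AIC can compare mean models only if the likelihoods are on a common footing. An ML likelihood is. A REML likelihood is that of the data after the fixed effects are removed, so it changes when the fixed effects change. The two codings have different fixed effects, so their REML AICs differ by an amount that depends on the outcome's units. Kenward-Roger inference is normally run on REML fits, so taking the AIC from the same REML output is a natural way to follow the text.

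At stake is which test answers the trial's title question. If the rule always returns 3-level coding, it no longer does what Protocol 11.4.2 intends, which is to let fit decide. A joint 2-df test would then spend a degree of freedom on departure from linearity, although the protocol's own assumed effects are exactly linear in the number of copies.

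**Working it through.** **1. The stated 61%.** Inputs from Protocol 11.2: N = 200 in a 1:1 ratio; 30%, 50% and 20% with 0, 1 and 2 LPS copies; treatment differences in net change of 1080, 540 and 0; SD 1190; alpha 0.05, taken as two-sided. The SD is given for the baseline index and is assumed here to apply to net change.

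- Weighted mean difference: 0.3 × 1080 + 0.5 × 540 + 0.2 × 0 = 594.
- Weighted variance: 0.3 × 1080² + 0.5 × 540² − 594² = 495,720 − 352,836 = 142,884.
- Noncentrality: (200/4) × 142,884 / 1190² = 7,144,200 / 1,416,100 = 5.045.

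Because the assumed effects are exactly linear, both tests have this noncentrality.

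| Test | df | Critical F | Power |
|---|---|---|---|
| Linear | 1, 196 | 3.889 | 60.8% |
| 3-level, joint | 2, 194 | 3.042 | 50.1% |

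The linear test reproduces 61%; the joint test does not. The gap stays near 10 points at other SDs (linear and joint: 75.8% and 65.8% at SD 1000; 53.4% and 43.0% at SD 1300) and at N = 180 (56.3% and 45.7%).

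**2. Parameter count.** The haplotype terms are a main effect, haplotype by treatment, haplotype by visit and the three-way term, with three visits.

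- Linear: 1 + 1 + 2 + 2 = 6.
- 3-level: 2 + 2 + 4 + 4 = 12.
- Difference: 6.

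**3. Effect of units.** Multiply the outcome by c. With n observations and p fixed effects, −2 log-likelihood rises by 2n ln(c) under ML and by 2(n − p) ln(c) under REML. Between the codings the ML change cancels. The REML change leaves 2 × 6 × ln(c) = 12 ln(c) in favour of the larger model.

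- c = 10: 27.63 units. Refitting one data set in both units gave 27.631 under REML and 0.000 under ML.
- c = 1190 (from SD units to raw units): 12 × 7.082 = 85.0 units.
- c = 10,000 (from a 0-1 scale to the plan's scale): 110.5 units.

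Protocol 2.5.1 multiplies two 0-100 scores, so the index runs from 0 to 10,000.

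**4. What the rule picks.** The first simulation used three visits, complete data, SD 1190, no covariates and the same effect at every visit, with all four candidate models. The non-additive shapes (1080, 0, 0 and 1080, 1080, 0) are assumptions.

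| AIC | Null or linear truth | Non-additive truth |
|---|---|---|
| REML, plan's units | 3-level in 100% | 3-level in 100% |
| REML, index ÷ 10,000 | linear in at least 99.98% | linear in 96-97% |
| ML, any units | linear in 93% | linear in 43-45% |

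In the plan's units the REML margin was 83 to 133 AIC units. A second simulation added site, sex, race and baseline at N = 180, with assumed between-visit correlations of 0.3 to 0.7. REML again chose 3-level coding in every run. Mean margins were about 89 to 96 units counting covariance parameters only, and 77 to 84 counting all parameters.

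**5. Error rate.** Each single test rejected in 4.8-5.1% of null trials. Choosing the coding by ML AIC and then testing (joint 2 df if 3-level) rejected in 5.8-5.9%.

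**6. Power after ML selection.** Under the linear gradient, ML selection followed by that test had 61.7% simulated power, against 61.5% for linear coding fixed in advance and 50.8% for the joint test fixed in advance.

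**The case against.** **The loss needs two things the plan does not state:** that the AIC is REML, and that a joint test follows. This stands. Under ML selection nothing is lost under the assumed gradient, and the protocol's stated aim of optimizing fit is what ML AIC would deliver. The point is therefore conditional, but the text allows either likelihood.

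**The contrast is less open than it looks.** A reader might infer that no Visit 4 test is specified. SAP 8.3.2 does specify one. With two dummy variables and a hypothesis that efficacy varies with the number of haplotypes, a joint 2-df test is the ordinary reading. Only the coefficients and degrees of freedom are missing. They still matter: a 1-df comparison of 0 with 2 copies would have 60.0% power, against 50.1% for the joint test.

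**Fit is not irrelevant in all units.** True. With the index divided by 1000 and all parameters counted, REML AIC chose 3-level coding in 3-22% of runs under a linear truth and 46-53% when only 0-copy carriers responded. The claim is limited to the plan's own scale.

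**Unmasking.** Because Protocol 11.4.1 says "Treatment allocation will be unmasked for further analyses", a reader might infer that these choices could be steered with treatment known. The documents do not support that charge. Protocol 11.4 has the SAP completed before database lock, SAP 8.3 keeps allocation masked until the primary analysis code is final, and an AIC rule is mechanical once written.

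**Pooling covariance and coding in one comparison** is legitimate under ML. The difficulty lies with REML only.

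**Conclusion.** The point holds as a should-fix clarification. If the AIC is REML, the rule returns 3-level coding in essentially every data set at the plan's scale. If a joint 2-df test follows, power under the assumed gradient is about 50%, not 61%.

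Two stronger readings are not supported. One is that the plan inflates false positives: each candidate test holds about 5%, and SAP 8.3.2 treats the analysis as supportive of the primary. The other is that the 61% is wrong: at SD 1190, the only SD documented, the linear test gives 60.8%. The documents do not name the test behind the figure; the joint test would reach 61% only at an SD near 1053, which appears in neither document.

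The power figures rest on the simplified one-observation inputs of Protocol 11.2. The simulations also assume complete data and the stated correlations, and the first used Satterthwaite degrees of freedom as an approximation to Kenward-Roger. The 12 ln(c) result is algebra and needs none of these assumptions.

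**What to change.** In SAP 8.3.2, replace the single AIC comparison with ordered steps:

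1. Under the same 3-level fixed effects, choose compound symmetry or unstructured covariance by REML AIC. Units do not affect this comparison.
2. With that structure, compare linear and 3-level coding by ML AIC.
3. Refit the chosen model by REML for the Kenward-Roger test.
4. State the Visit 4 interaction test: 1 df if linear, joint 2 df if 3-level.

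Bring SAP 8.3.3 into line, so that it no longer describes the LPS model as linear in advance. Beside the 61% in Protocol 11.2 and SAP 2.6, note that it corresponds to the linear 1-df test at SD 1190, and that the joint 2-df test has about 50%.

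The cost is wording only; no new data are needed. The small statistical price is a type I error of about 6% after selection. In return the rule keeps power if the effect is not additive. In simulation it had 76.6% when only 0-copy carriers respond and 62.9% when 0- and 1-copy carriers respond equally, against 69.0% and 51.1% for linear coding fixed in advance.

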## 4 STUDY ENROLLMENT AND WITHDRAWAL

### 4.1 Participant Inclusion Criteria

A participant must meet all of the following inclusion criteria to be eligible for initial enrollment and randomization:

- 1) Provides a signed and dated informed consent form
- 2) Is between 18 and 65 years of age (inclusive; male or female and any race or ethnicity)
- 3) Meets diagnostic criteria for TMD, Group II: Masticatory Muscle Disorders, 1A: Myalgia
- 4) Has experienced facial pain for at least 3 months
- 5) Has experienced facial pain for at least 10 days of the last 30 days
- 6) At Screening and Baseline Visit (Visit 0), reports an average pain intensity rating over the past week of  $\geq 30$  on a numerical rating scale (0-100)
- 7) At randomization (Visit 1), has satisfactorily completed at least 4 entries per week in the Daily Symptom Diary within the preceding week and reported an average pain intensity score  $\geq 30$  on a numerical rating scale (0-100) or reports a rating of average daily pain intensity of  $\geq 30$  on the same scale on at least 3 days over the past week
- 8) If taking a prescription medication (with the exception of prescription formulations of NSAIDs, acetaminophen, and aspirin) episodically (or as needed) for the management of pain, agrees to discontinue its use prior to or at the Screening and Baseline Visit
- 9) If taking a prescription medication daily for the management of pain, agrees to continue the daily use of the medication throughout the study
- 10) If taking an over-the-counter pain medication daily, agrees to continue the daily use of the medication throughout the study
- 11) Agrees to not commence any new prescription medication for the management of pain throughout the study
- 12) Agrees to not commence any injection therapy for pain (e.g., tender or trigger point injections, steroid injections) during the course of the study
- 13) Agrees to not use acupuncture, biofeedback, or transcutaneous electrical nerve stimulation (TENS) for the management of pain during the course of the study
- 14) Agrees to not commence occlusal splint therapy during the course of the study
- 15) Agrees to continue use of splint therapy if commenced more than 30 days previously

---

- 16) Females agree to limit consumption of alcohol to no more than 7 drinks\* and males agree to limit consumption of alcohol to no more than 14 drinks\* a week for the duration of the study

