## **5.7 Concomitant Medications and Therapies**

Prior and concomitant medication information will be collected for all participants for the 30 days prior to the Screening and Baseline Visit and during the study. Information collected will include medication, total daily dose, start date, stop date (if applicable), and primary reason for use. Information about treatment with injection therapy, acupuncture, biofeedback, TENS, and occlusal splint therapy will also be collected for all participants for the 30 days prior to the Screening and Baseline Visit and during the study.

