### **5.7.1 Rescue Medication**

Rescue medications described below may be used to alleviate pain. Episodic use of a rescue medication will be defined as use for no more than 3 consecutive days and for no more than 18 total days from Visits 1 to 4.

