#### **5.7.1.1 Over-the-counter medications**

NSAIDs are most often used to manage pain in TMD patients. If a participant is taking an over-the-counter medication daily for pain management, the participant will be encouraged to continue the same usage of that medication throughout the study. The usage of short-acting, non-prescription analgesics (e.g., NSAIDs, aspirin, and/or acetaminophen) by participants during the study will be recorded and quantified at each visit, and the usage will be classified as either daily or episodic.

---

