The participants' use of rescue medications for TMD pain as well as over-the-counter analysis as well as over-the-counter analysis as well as over-the-counter analysis. (namely, NSAIDs, acetaminophen, and aspirin) for the treatment of any type of pain during a period from V1 to V4 will be summarized by treatment group, both overall and by study visit. The number of days on over-the counter analgesics and the number of days on over-the counter analgesics as a ratio of days on study drug will be summarized (n, mean and standard error) by treatment group, both overall and by study visit. Log-transformed linear regression models will test for treatment group effects on the total number of days a participant is on rescue medications for the treatment of TMD-related pain and (in a separate analysis) for over-the-counter analgesics for the treatment of any pain. The days on rescue medications (or over-the-counter analgesics for any pain) will be log-transformed and used as the dependent variable. If there are some participants with 0 days on rescue medications (or over-the-counter analgesics), then a log(x+1) transformation of days will be used to prevent log(0) values. Study site, mean pain index at V1, and days on study (log-scale) will be used as covariates in the statistical models. Adjusted mean estimates and their 95% confidence intervals of the model adjusted days on rescue medications (or analgesics for any pain) will be reported with their treatment group effect p-values. If residual analysis suggests that model assumptions are unreasonable, then the following alternative model will be used to test for treatment group effects on the use of rescue medications (or over-the-counter analgesics for any pain). This alternative model will be a generalized linear mixed model using a negative binomial link with days on rescue medications (or over-the-counter analgesics for any pain) as the dependent variable and covariates for study site, mean pain index at V1, and for days on study.

Version 3.0 Page 16 of 25

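### The analgesic-day models do not adjust for daily analgesic use ongoing at Visit 1; one baseline indicator would sharpen the log-linear test and mainly recalibrate the standard error of the fallback.

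*SAP*

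**What the plan says.** SAP 8.3.2 analyses two counts from Visit 1 to Visit 4: days on rescue medication for TMD pain, and days on OTC analgesics (NSAIDs, acetaminophen, aspirin) for any pain. The main model is a linear regression of log days, or log(days+1) if there are zeros. Its adjustment is: "Study site, mean pain index at V1, and days on study (log-scale) will be used as covariates in the statistical models". If the residuals look unreasonable, a negative binomial model replaces it, with "covariates for study site, mean pain index at V1, and for days on study". Protocol 11.4.2 names no covariates and refers to the SAP.

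Daily analgesic users may enter. Protocol 4.1 criterion 9 reads: "If taking a prescription medication daily for the management of pain, agrees to continue the daily use of the medication throughout the study". Criterion 10 reads: "If taking an over-the-counter pain medication daily, agrees to continue the daily use of the medication throughout the study". Protocol 5.7.1.1 and 5.7.1.2, both under the Rescue Medication heading, encourage the same. Someone using a prescription pain drug only as needed (NSAIDs, acetaminophen and aspirin excepted) instead "agrees to discontinue its use prior to or at the Screening and Baseline Visit" (criterion 8).

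On the data, Protocol 5.7 records drug, total daily dose, "start date, stop date (if applicable), and primary reason for use", from 30 days before Visit 0 onward; Visits 0 and 1 both record concomitant medication (6.2, 6.3.1). During the study, OTC use is "recorded and quantified at each visit, and the usage will be classified as either daily or episodic" (5.7.1.1). Episodic use is defined only for the treatment period: at most 3 consecutive days and "no more than 18 total days from Visits 1 to 4" (5.7.1).

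Less frequent rescue and OTC use is part of the secondary hypothesis in Protocol 11.1.2. SAP 8.3.2 calls these analyses supportive of the primary one, tests them at 0.05 without multiplicity correction, and drops about 20 early UB participants from the rescue model because their type of pain was not recorded.

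**The concern.** A participant who enters on a daily analgesic and keeps to the agreement will have a high day count in either arm. That part of the outcome is fixed before the first dose and is largely unrelated to treatment, yet no covariate represents it. Visit 1 pain index is not a substitute for medication habit, and randomisation is stratified by site only (Protocol 4.4.1), so daily use is not balanced by design. The other continuous and count secondary measures are analysed as change from baseline; these two carry no baseline of their own.

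In a linear model, between-person differences of this kind stay in the error term and widen the interval for the treatment effect. A null result could then be read as no analgesic-sparing effect when the model was simply noisier than it had to be.

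**Working it through.** **No plan figure to reproduce.** The documents give no power, spread, effect size or daily-user share for the analgesic-day outcomes. Everything below rests on assumed inputs, shown over a range.

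**Formula.** For a baseline yes/no factor with prevalence p, independent of arm, leaving it out of a linear model multiplies the variance of the treatment estimate by 1/(1−R²), where R² = p(1−p)(m_daily − m_other)² / total variance and m is mean log(days+1). Illustration, assuming 10% daily users on 90% of days and others averaging 8 of 63 days (negative binomial dispersion 0.7): R² = 0.329, so variance is multiplied by 1/0.671 = 1.49 and the interval is √1.49 = 1.22 times as wide.

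**Simulation of the SAP log-linear model** (6,000 trials per scenario).
- From the documents: 200 − 20 = 180 participants for rescue and 200 for OTC; 10% dropout (Protocol 11.2); covariates as in SAP 8.3.2.
- Assumed: non-daily users average 10 days, dispersion 0.5, rate ratio 0.6 on drug, log-rate slope 0.2 per SD of pain index; daily users take analgesics on 80% of days on average, with no benefit; 63 to 69 days on study, with dropouts spread evenly over days 7 to 62. Misclassification is 10% in both directions.

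Rescue model, N = 180:

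| Daily users | Variance cut, correct | Variance cut, 10% misclassified | Power as planned | Power, correct | Power, 10% misclassified |
|---|---|---|---|---|---|
| 5% | 17% | 4% | 39% | 46% | 40% |
| 10% | 30% | 11% | 33% | 44% | 36% |
| 20% | 46% | 24% | 25% | 40% | 31% |
| 30% | 56% | 33% | 18% | 35% | 25% |

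Interval width follows as 1 − √(1 − cut): a 30% cut gives 1 − √0.70 = 16% narrower, and an 11% cut gives 1 − √0.89 = 6% narrower. The OTC model (N = 200) gives 17%, 30%, 46%, 56%, and 4%, 12%, 24%, 33% with misclassification. Type I error is 4.9% to 5.3% as planned and 4.8% to 5.5% with the indicator, so the planned test is valid.

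**Sensitivity.** If daily users benefit equally, the cuts are 14% to 50% (3% to 30% misclassified). If 30% of them stop after Visit 1, 9% to 29% (2% to 17%). Over all log-linear runs the range is 9% to 71%, or 2% to 42% misclassified. The indicator must match the outcome: in the rescue model, with 10% daily for TMD pain plus 10% or 20% daily for other pain only, an any-pain indicator cuts 13% or 8% instead of 30%.

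**Negative binomial fallback, same inputs.** True spread (SD) of the estimate under no effect, without and with the indicator, at 5%, 10%, 20%, 30% daily users: 0.219 and 0.207; 0.199 and 0.198; 0.184 and 0.189; 0.169 and 0.173 (about 600 trials each). There is no material gain in precision. The model-based standard error, however, is too wide when daily users are common: at 30%, separate runs give 0.206 against a true 0.163 (0.206/0.163 = 1.26) and 0.209 against 0.146 (1.43). Rejection under the null (3,000 trials per scenario) is 4.2%, 4.6%, 2.4%, 1.6% as planned; 5.4% to 6.6% with a correct indicator; 4.2% to 4.8% with 10% misclassified. If daily users benefit equally, power is 63%, 63%, 66%, 72% as planned and 66%, 68%, 77%, 83% with a correct indicator.

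**The case against.** The plan contains no error. The test is valid, the analyses are supportive, and Protocol 11.4.2 leaves the model to the SAP, so adding a prognostic covariate is an efficiency gain and not a repair. That stands, and it limits how hard the point can be pressed.

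A reader might infer that 17% to 56% of the variance can be recovered whichever model is reported. The documents do not support this. The SAP switches models if residuals are unreasonable, and under the inputs above 18% to 25% of participants have zero days while daily users cluster near the maximum. A Shapiro-Wilk test rejects normal residuals in 99% to 100% of planned fits, and in 90% to 98% even with the indicator. The SAP names no residual test, so this is illustrative, but the switch is plausible, and in the fallback the precision gain largely disappears. Calibration there is already close to nominal at 5% to 10% daily users, and at 20% to 30% the planned model errs on the conservative side.

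A reader might also infer that baseline daily use is already a recorded field. Protocol 5.7 lists none, the classification in 5.7.1.1 is of use during the study, and the eligibility criteria are agreements, not data items. Daily use has to be derived, so the misclassified figures are the safer guide.

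Finally, a reader might take the rescue model to be as clear a case as the OTC model. It is not: the layout of Protocol 5.7.1 suggests that ongoing daily medication is rescue, but the SAP never says that such days are counted.

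**Conclusion.** The point holds as a cheap improvement to two supportive secondary analyses, firmest for OTC use and conditional for rescue use. There is no bias and no effect on the primary analysis. If the log-linear model is kept, the variance cut is about 4% to 33% with 10% misclassification and 17% to 56% at best, for an assumed 5% to 30% daily users. If the fallback is used, the benefit is mainly a better calibrated standard error from about 20% daily users upward. The size depends on assumed shares, day counts, dispersion and effect, and is small if daily users are few or poorly identified. Under the inputs shown, log-linear power stays at or below 46% even with perfect classification, so the change does not make this a well-powered test. Nor does it undo the dilution from participants whose use is unlikely to change.

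**What to change.** Before treatment is unmasked (Protocol 11.4.1 unmasks it for the analyses after the primary one), amend SAP 8.3.2 as follows.

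- Add one prespecified yes/no indicator of daily analgesic use ongoing at Visit 1 to both the log-linear model and the negative binomial fallback.
- Derive it from concomitant medication records up to Visit 1: drug, total daily dose, start and stop dates, and reason for use. Write down what counts as daily at baseline, since the definition of episodic use in Protocol 5.7.1 covers only Visits 1 to 4. Require a start before Visit 1 and no stop date on or before Visit 1; episodic prescription use stopped under criterion 8 is then not counted.
- OTC model: daily NSAIDs, acetaminophen or aspirin for any pain. No pain type is needed, so the roughly 20 UB participants stay in.
- Rescue model: first state whether ongoing daily medication counts as rescue days. If it does, the indicator is daily use for TMD pain of any drug counted as rescue.

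The cost is some blinded coding of records already collected and one degree of freedom per model. If the indicator proves uninformative, the loss is about 0.6% of precision: with 180 participants and six coefficients, 1/(180 − 6) = 0.6%. Nothing changes in treatment, visits or data collection.
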